## 4.2. Patient screening and randomization

Patients are recruited upon presentation and recruitment is based on the stage of melanoma.

Stage IB-III patients will be enrolled from fall 2012 to fall 2023.

After staging and surgical treatment, and after obtaining written informed consent, patient will undergo screening at the investigational site to ensure that the patient meets all other in- and exclusion criteria. Written informed consent must be obtained from patients prior to any study specific procedure (for details see section 8.1). After consenting patients undergo the procedures listed for the screening visit. If the patient meets all in- and exclusion criteria, the patient will then be randomized using a specifically designed Interactive Voice Response system (IVRS) on an equal basis (1:1) to either vitamin D or placebo stratified on time of diagnosis (newly diagnosed, 0-6 months or 6-12 months before start of the study). The IVR system will supply a patient number that will be used as the key identifier for the entire study period. Patients in both arms will receive similar looking capsules, containing either 100 000 IE cholecalciferol or placebo oil. The randomization schedule will be kept under closure at the data management centre. All other study staff members, dermatologists, trial nurses, and patients will be blinded to the treatment allocation. The DSMB members may be unblinded to assess the safety of the patients. The study complies with the Helsinki declaration of medical research and needs approval by the hospital medical ethics committee. Written informed consent will be obtained prior to enrolment.

In these stage IB-III melanoma patients (500 patients), we will take a blood sample for serum analysis (25(OH)D3 levels) at the moment of diagnosis and, every 6 months until relapse or until the end of the study.

Every participant will also be asked to complete a questionnaire regarding melanoma risk factors, including amount and type of sun exposure and to undergo skin examination for the assessment of phototype, naevus phenotype and actinic damage. We will measure patient's height and weight, which will be used to estimate body mass index (BMI).

Our power calculations are based on a patient enrolment rate of 500 melanoma patients until the end of the study. In order to meet those targets, a multicentre study is necessary, via participation of other academic centers.

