### 2.2. Secondary objective

Secondary efficacy endpoints are:

- Melanoma subtype, as assessed clinically and histologically
- Melanoma site, as clinically recorded
- 25(OH)D3 serum levels at diagnosis and at 6 months intervals
- Stage of melanoma patient at diagnosis according to the 2009 AJCC Melanoma staging and classification

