### **3. OVERALL DESIGN AND PLAN OF THE STUDY**

#### **3.1. Overview of study flow**

To investigate whether vitamin D supplementation after diagnosis affects malignant melanoma outcome (primary endpoint relapse free survival), stage IB-III patients will be enrolled from fall 2012 to fall 2023. Stage IA patients will not be included in the study because they only have a very small chance to relapse. This double-blind randomized study will comprise 500 patients (stage IB-III). This patient cohort will be randomized in a 1:1 ratio to vitamin D supplementation or placebo. We will also assess the expression of the Vitamin D Receptor (VDR) expression in the primary tumor. A blood sample will be taken for DNA analysis (genetic variability in the vitamin D pathway). We will check 25(OH)D3 serum levels both at diagnosis, and every 6 months until the end of the study. This patient cohort will exist of 3 subgroups (patients diagnosed within 6 or 12 months before start of the study and newly diagnosed patients). Inclusion of previously diagnosed patients will allow us to assess whether delayed supplementation has a similar effect on the relapse free survival rate as immediate supplementation after surgery of the tumor.

In this randomized vitamin D supplemented placebo-controlled trial (both arms), we will assess whether vitamin D supplementation in the follow up period after diagnosis has a protective effect on relapse (primary endpoint) of the malignant melanoma and whether this protective effect correlates with the vitamin D receptor immunoreactivity in the primary tumor.

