**Table 1: Schedule of assessments**

	Screening	Randomization = day 0	Every 3 months FU	Every 6 months FU	End of Study (fall 2023) or Progression/Relapse
Informed Consent	X				
Demographics	X				
Medical History	X				
Melanoma Risk Factors	X				
Sun exposure Behaviour	X				X
Physical Examination	X		x		X
Vitamin D levels		X		X	X
DNA analysis		x			
Safety Laboratory#	X		X	x	X
Concomitant Medications	X	X	X		X
Adverse Event / Endpoint Collection		X	X		X
24 hour urine calcium					X

+

#

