#### 4.3.4. Clinical laboratory

Blood sampling and sample analysis is performed at the clinical centre. The local investigator is responsible for proper judgment of abnormal blood test results, and is responsible to appropriate patient care following clinically relevant pathological results. Please refer to section 6.4.4 to determine whether an abnormal laboratory value may constitute an adverse event.

The following analysis is to be obtained:

Screening and end of study:

- Hematology: hemoglobin, hematocrit, WBC count with differential, RBC count and platelet count
- Biochemistry and enzymes: serum creatinine, serum calcium, serum phosphate, AF, ALT, gamma GT, LDH

Randomisation (Day 0):

- Baseline serum vitamin D level.
- Bloodsample for DNA analysis

Every 3 months:

- serum calcium
- serum phosphorus
- 25(OH)D3 serum levels, in case of drug interruption when serum 25(OH)D3 levels are > 80 ng/ml

Every 6 months:

- 25(OH)D3 serum levels
- WBC plus differential

End of study: 24 hrs urine calcium

SNP analysis will be performed by the laboratory of [name], VIB

Peripheral blood from study participants will be sampled in K2EDTA tubes.

The samples are coded and only then transferred to VIB. So VIB only has coded information from the patients. Subsequently, tubes will be transferred to the Vesalius Research Center (Leuven) and genomic DNA will be extracted by a standard salting out method and stored at -80 °C until further analysis. Genetic variants affecting VD levels will be genotyped in a blinded manner using iPLEX technology on a MALDI-TOF based MassARRAY Compact Analyser (Sequenom Inc., CA, USA). The Sequenom's iPLEX technology efficiently multiplexes up to 32 different SNP's in one PCR reaction, thereby providing rapid and accurate SNP genotypes at an affordable price. Only samples for which ≥ 80% SNPs have succeeded will be considered for further analysis. SNPs with a call rate < 98% will be re-designed and genotyped again to reach success rates close to 100%. At least 5% of the samples will be genotyped in duplicate, to prove accuracy of the genotyping protocol. We expect that approximately 2 Sequenom assays will have to be applied on the DNA of participating individuals to cover all 19 SNPs. Multiple Single Nucleotide Polymorphisms (SNPs) have been reported to affect VD signaling.

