### **7.2. Statistical Methods**

The primary analysis is an intent-to treat analysis of all randomised patients. Patients will be analysed according to the treatment group to which they were randomised, irrespective of which study drug was given or if any study drug was received. Additional populations like a per protocol population may be defined in the statistical analysis plan

The difference in relapse-free survival will be compared between the two treatment groups by means of a Cox proportional hazards model stratified for time since diagnosis (3 strata: 0, 6 or 12 months ago). It will be verified whether the treatment effect is stratum dependent. If so, the strata will be analysed separately. Furthermore, using a Cox proportional hazards model it will be investigated whether the potential treatment effect is different for VDR immunoreactivity and genetic variability in the Vitamin D pathway. A correction for other baseline covariates like gender, age and

baseline Vitamin D level will be performed as sensitivity analyses. No interim analysis for efficacy is foreseen. Potential subgroups analysis like for instance calcium serum levels will be defined in the statistical analysis plan

The evolution in 25(OH)D3 levels in function of genetic variability in the Vitamin D pathway will be analysed by a linear mixed model. Sensitivity analyses will include patient's compliance, seasonal effects and patient's baseline characteristics like age and gender.

In order to examine the effect of the actual 25(OH)D3 levels rather than just supplementation, the evolution of 25(OH)D3 levels and relapse-free survival will be jointly modelled.

The potential correlation between VDR immunoreactivity and stage at diagnosis will be assessed by means of a Kruskal Wallice test.

The potential correlation between vitamin D levels at diagnosis with melanoma site and melanoma subtype will be assessed by means of an analysis of variance. This analysis can only be performed for newly diagnosed patients because vitamin D levels at diagnosis will not be available for patients who had their diagnosis 6 or 12 months ago.

Full details of the statistical analyses will be described in a statistical analysis plan which will be finalized before database lock.

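### 25(OH)D3 at diagnosis is a secondary endpoint, but the first scheduled sample is at randomisation, after surgery, so the site and subtype analysis would report a post-surgical baseline level as a level at diagnosis

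*Combined protocol and SAP*

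**What the plan says.** The protocol describes the first 25(OH)D3 measurement in two ways.

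**As a level at diagnosis.** The synopsis and section 2.2 list as a secondary endpoint "25(OH)D3 serum levels at diagnosis and at 6 months intervals". Section 3.1 states "We will check 25(OH)D3 serum levels both at diagnosis, and every 6 months until the end of the study", and section 3.2 repeats it. Section 4.2 says that all 500 patients are sampled "at the moment of diagnosis and, every 6 months until relapse or until the end of the study". Item 4 of the added-value list in section 1.1 makes the correlation of this level with site and subtype a stated aim. Section 7.2 plans an analysis of variance for it.

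**As a baseline level at randomisation.** In Table 1 the first vitamin D sample stands in the column headed "Randomization = day 0". Section 4.3.4 lists under day 0 the item "Baseline serum vitamin D level".

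Section 7.2 sees part of the problem: "This analysis can only be performed for newly diagnosed patients because vitamin D levels at diagnosis will not be available for patients" diagnosed 6 or 12 months earlier.

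**The concern.** A secondary endpoint is defined at a time when the schedule collects nothing. Section 7.2 treats this as a gap only for patients diagnosed months before entry. The newly diagnosed are handled as though they had been sampled at diagnosis, yet they reach day 0 by the same route as everyone else.

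What is at stake is the meaning of one secondary result. The trial would report how vitamin D status at diagnosis relates to tumour site and subtype, using blood drawn after the diagnosis was known and the tumour removed. Season will have moved on by then, and sun exposure or supplement use may have changed.

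**Working it through.** The point concerns when a sample is taken. The plan gives no figure to reproduce, so the check sets the sections side by side.

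1. **Order of events (section 4.2).** "After staging and surgical treatment, and after obtaining written informed consent, patient will undergo screening at the investigational site"; randomisation follows screening. The same section adds: "Written informed consent must be obtained from patients prior to any study specific procedure". A study blood sample therefore cannot precede consent, and consent comes after staging and surgery.

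2. **First sample (Table 1, section 4.3.4).** Table 1 has no diagnosis column and no vitamin D entry at screening. The first entry is at day 0, and section 4.3.4 agrees. The schedule thus yields one initial value per patient. Section 7.2 gives that value two names: a baseline level when it is a covariate in the sensitivity analyses, and a level at diagnosis when it is the outcome in the analysis of variance.

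3. **Internal conflict on availability.** Section 4.2 promises a sample at diagnosis for all 500 patients. Section 7.2 says there will be none for those diagnosed 6 or 12 months ago. Both cannot be right.

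4. **Length of the lag.** Lag = date of day-0 sample minus date of diagnosis.
   - Lower end: above zero, because staging, surgery, consent and screening all fall in between.
   - Upper end, all patients: about 12 months, from the inclusion criterion in section 3.3.2 (entry within 1 year of diagnosis).
   - Upper end, newly diagnosed: not stated. Sections 3.2 and 4.2 list this group beside a 0-6 month and a 6-12 month group without separating it from the 0-6 month group. Sections 7.1 and 7.2 code it as 0 months. If the strata are counted back from each patient's own entry, the separate 6-12 month stratum implies a ceiling of about 6 months. Otherwise only the 1-year limit applies.

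5. **Adjustment.** Section 7.2 names seasonal effects among the sensitivity analyses of the mixed model for the evolution of 25(OH)D3. For the site and subtype analysis it names neither season nor time since diagnosis.

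**The case against.** The case for leaving the plan alone has several parts.

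- **The restriction to newly diagnosed patients removes the known long lags.** It does, and that is a real protection. It does not turn the remaining values into levels at diagnosis, and with no window the lag left in that group is unknown.
- **Some relevant data are collected.** Table 1 records sun-exposure behaviour at screening and concomitant medication at screening and day 0. That helps, but section 7.2 does not link either to this analysis.
- **Details are deferred to an analysis plan due before database lock.** That plan can add covariates, but it cannot supply a sample that was not scheduled.
- **Day 0 is the natural baseline** for the 25(OH)D3 evolution model and the joint model. This stands; neither is criticised here.

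A reader might also infer more than the documents support:

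- *That the sample is taken after randomisation.* Table 1 and section 4.3.4 put it at randomisation; the order within day 0 is not given.
- *That the delay is unlimited.* The 1-year inclusion limit caps it.
- *That the delay grows with stage and so biases the subtype comparison.* Section 4.3.2 offers sentinel biopsy to node-negative patients at intermediate or high risk, so that step does not mark node-positive disease. Only the further imaging and lymphadenectomy after a positive node do, and no durations are given. Longer lag in node-positive patients is plausible; a resulting site or subtype bias is not shown.
- *That seasonal drift sizes the error.* Suppose, with no source in the documents, a sinusoidal swing P of 8 to 12 ng/ml peak to trough. The largest change over d months is P × sin(πd/12): 8 × 0.5 = 4.0 to 12 × 0.5 = 6.0 ng/ml at 2 months, and 8 × 0.707 = 5.7 to 12 × 0.707 = 8.5 ng/ml at 3 months. These are worst cases for a single patient. Across diagnosis dates spread evenly over the year the change averages zero, so drift mainly adds noise. A false difference by this route would need lag and seasonal accrual both to differ by group. A true sample at diagnosis would also vary by season between patients.
- *That no level at diagnosis could exist.* The documents do not say whether routine results from before consent are held, and do not plan to use any.

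**Conclusion.** The point holds as a mismatch between a stated secondary endpoint and the schedule meant to deliver it. No sample at diagnosis is scheduled, and the site and subtype analysis would label a post-surgical baseline value as one. This follows from the protocol's own text and needs no outside assumption.

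Its size is limited. It concerns one secondary analysis that makes no treatment comparison. Relapse-free survival is unaffected. The lag in newly diagnosed patients is above zero and otherwise unspecified, within about 6 or 12 months depending on how the strata are read. Neither the size nor the direction of any site or subtype bias can be determined from the documents. The labelling should nevertheless be corrected, because the conclusion would otherwise describe a quantity that the schedule does not provide.

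**What to change.** 1. Call the value 25(OH)D3 at baseline (day 0, after surgery) wherever the protocol now describes it as a level at diagnosis: synopsis, section 1.1 (the added-value item on vitamin D, site and subtype), 2.2, 3.1, 3.2, 4.2 and 7.2. Stage at diagnosis, and the description of the cited observational study, stay as they are.
2. Define newly diagnosed by a maximum number of days from diagnosis that does not overlap the 0-6 month stratum, and use that definition in every section.
3. Derive days from diagnosis to the day-0 sample for each patient.
4. Include that lag and the month or season of sampling as covariates in the site and subtype analysis.
5. Word the conclusion as an association with the post-surgical baseline level.

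Two further steps are not advised. Restricting the analysis to patients sampled within an arbitrary few weeks could select on stage if node-positive patients take longer to reach day 0. Filling in routine pre-operative results where a site happens to hold them would mix sources and select on local practice.

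The cost is consistent wording, one derived variable (time since diagnosis is already needed for stratification), two extra model terms and a less ambitious claim for one secondary analysis. The covariates can go into the statistical analysis plan, which section 7.2 says will be finalised before database lock.

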### 4.3. Description of study assessments

#### 4.3.1. Medical history / demographics

A complete medical history is obtained from each patient at the screening visit. Demographics, including gender, age and country of birth of all four grandparents, and the smoking status are recorded.

#### 4.3.2. Staging of melanoma

Patients are ranked according to the following staging system:

**Pathological staging of the primary tumor:** is performed at the department of Pathology of the participating centers and is based on the Breslow thickness of the tumor, mitotic rate and presence or absence of ulceration. Breslow thickness of the tumor is measured by a calibrated eye piece graticule, and reflects the distance from the granular layer of the epidermis to the deepest tumor cell in millimetres. Mitotic rate is determined by the hot spot approach (as recommended by the melanoma Staging Committee) and expressed as the number of mitoses per square millimetre (i.e. 11 high power fields) of primary tumor. Presence or absence of ulceration is determined on Hematoxilin and Eosin sections.

**Staging for regional metastatic melanoma:** is performed by routine physical examination, including palpation of the lymph nodes and ultrasound examination of the lymph node regions. Ultrasound of the drainage region with FNAC for cytological evaluation will be performed in patients with suspicious nodes by ultrasound. In case of lymph node metastasis PET-CT and brain MRI is performed to exclude general metastatic loci, and patients undergo a complete lymphadenectomy.

Patients with negative nodes (clinically and by ultrasound) but with primary tumor pathology at intermediate or high risk for tumor metastasis (Breslow  $> 1$  mm or  $\leq 1$  mm but with ulceration and/ or mitosis  $\geq 1/\text{mm}^2$ ), are candidate for lymphatic mapping with sentinel lymph node biopsy. When the sentinel node is positive these patients will have a PET-CT and brain MRI to exclude general metastatic loci, and undergo a complete lymphadenectomy.

Nodal micrometastasis are detected by routine H&E staining, supplemented by immunohistochemistry with a cocktail of antibodies directed against Melan-A, tyrosinase and gp100 (HMB45). Processing of the sentinel node and reporting of the results will be done according to EORTC guidelines. Stage IB-III patients are eligible for the vitamin D supplementation study if the only treatment is surgery. (Mohr et al, 2009).

#### 4.3.3. Follow-up for relapse

Patients are taught the process of self-examination; Follow-up intervals are three-monthly. Since up to 70% of the first recurrence is found in the loco regional area, follow up visits will consist of routine physical examination, including full skin assessment and palpation of regional lymph nodes. Ultrasound of the lymph nodes will be performed in all patients at an interval of 6 months, or in case of palpable lymph nodes. Ultrasound of draining lymph nodes by experienced radiologists has higher sensitivity to detect relapse compared with clinical examination. (PET)CT to exclude distant metastasis and MRI to exclude brain metastasis will be performed in patients with new symptoms and physical findings. Routinely PET(CT) and MRI are not used in the follow up period, since there is lack of prospective studies proving the efficacy of these expensive imaging techniques in routine follow up. Since both arms in the study are followed identically, the primary endpoint of the study will not be hampered by this less invasive and aggressive follow-up approach. (Mohr et al, 2009) (Garbe et al, 2012).

#### 4.3.4. Clinical laboratory

Blood sampling and sample analysis is performed at the clinical centre. The local investigator is responsible for proper judgment of abnormal blood test results, and is responsible to appropriate patient care following clinically relevant pathological results. Please refer to section 6.4.4 to determine whether an abnormal laboratory value may constitute an adverse event.

The following analysis is to be obtained:

Screening and end of study:

- Hematology: hemoglobin, hematocrit, WBC count with differential, RBC count and platelet count
- Biochemistry and enzymes: serum creatinine, serum calcium, serum phosphate, AF, ALT, gamma GT, LDH

Randomisation (Day 0):

- Baseline serum vitamin D level.
- Bloodsample for DNA analysis

Every 3 months:

- serum calcium
- serum phosphorus
- 25(OH)D3 serum levels, in case of drug interruption when serum 25(OH)D3 levels are > 80 ng/ml

Every 6 months:

- 25(OH)D3 serum levels
- WBC plus differential

End of study: 24 hrs urine calcium

SNP analysis will be performed by the laboratory of [name], VIB

Peripheral blood from study participants will be sampled in K2EDTA tubes.

The samples are coded and only then transferred to VIB. So VIB only has coded information from the patients. Subsequently, tubes will be transferred to the Vesalius Research Center (Leuven) and genomic DNA will be extracted by a standard salting out method and stored at -80 °C until further analysis. Genetic variants affecting VD levels will be genotyped in a blinded manner using iPLEX technology on a MALDI-TOF based MassARRAY Compact Analyser (Sequenom Inc., CA, USA). The Sequenom's iPLEX technology efficiently multiplexes up to 32 different SNP's in one PCR reaction, thereby providing rapid and accurate SNP genotypes at an affordable price. Only samples for which ≥ 80% SNPs have succeeded will be considered for further analysis. SNPs with a call rate < 98% will be re-designed and genotyped again to reach success rates close to 100%. At least 5% of the samples will be genotyped in duplicate, to prove accuracy of the genotyping protocol. We expect that approximately 2 Sequenom assays will have to be applied on the DNA of participating individuals to cover all 19 SNPs. Multiple Single Nucleotide Polymorphisms (SNPs) have been reported to affect VD signaling.

Following SNPs of the VDR will be determined: rs2228570 (Fok1), rs731236 (Taq1), rs1544410 (Bsm1), rs7975232 (Apa1), rs757343 (Tru91). Following 14 SNP's of the VD pathway genes will be determined: rs12785878 (DHCR7 gene), rs10741657 (CYP2R1 gene), rs59443548, rs1803361 rs2229381, rs11559242, rs41272685, rs41272687 (6 SNP's of CYP27A1 gene), rs10877012 (CYP27B1), rs2296241, rs2248359, rs6013897 (CYP24A1), rs4588, rs7041 ( 2 SNPs for DPB gene). The SNP analysis will be in collaboration with the laboratory of [name].

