## PROTOCOL SYNOPSIS

Title	The ViDMe Project "Vitamin D supplementation in cutaneous malignant melanoma outcome"
EudraCT No.	2012-002125-30
Phase	III
Sponsor	UZ Leuven
Coordinating Investigator	[name]
Study Objectives	To assess whether vitamin D supplementation, in the follow up period after diagnosis and surgery of the primary tumor, has a protective effect on relapse of cutaneous malignant melanoma and whether this protective effect correlates with vitamin D levels in serum and vitamin D receptor (VDR) immunoreactivity in the primary tumor.
Design	double-blind randomized placebo-controlled study
Treatment Groups	Group 1: optimal standard of care (control group) Group 2: high dose vitamin D3 supplementation added on top of optimal standard of care. Patients will be randomised to treatment or control group in a 1:1 ratio.

Study Flow and Assessments	
The study is divided into three parts:
 

• Screening phase: Patients are recruited at the Departments of Dermatology, Oncosurgery or Medical Oncology at the University Hospitals Leuven (Belgium), and other European academic sites. If all eligibility criteria are met, patients are then randomized to the treatment or control group. Randomisation is completed via IVRS. Patients are randomized as they come.

• Treatment phase: Vitamin D3 supplementation is given to the patients assigned to the treatment group and placebo to the control group in a double blind manner. Every participant is expected to take in the study drug orally once each month. Study duration is a maximum of 3.5 years or until relapse occurs.

• Follow-up phase: Every participant will be followed up every 3 months up to the final study visit. Endpoints will be reported as occurring throughout the follow up. Defined endpoints are adjudicated by an independent Clinical Endpoint Committee (CEC) blinded to the patient treatment allocation. This ensures a consistent and unbiased adjudication of events.

 
Study data are reviewed by a Data and Safety Monitoring Board (DSMB) that reviews key safety data on an ongoing basis.

-----------------------------------	--

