#### **4.3.9. Duration of the whole study**

Our power calculations are based on a patient enrolment rate of 500 melanoma patients during a recruitment phase of three years maximum. Concerning the enrolment period: the first patient will be recruited as of fall 2012 and the last patient in fall 2023. In order to meet those targets, a multiple center study is necessary, via participation of other academic centers.

The DSMB may terminate the study earlier based on safety concerns at any time. The sponsor may also terminate the study early for reasonable cause. Competent authorities/ethics committees retain the right for premature termination of the study according to applicable regulations. The study may also be terminated early if the work performed is not compliant with Good Clinical Practice.

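### Section 4.3.4 reads as local 25(OH)D3 measurement, yet no level analysis in section 7.2 has a centre or laboratory term, so centre can confound the non-randomised level associations

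*Combined protocol and SAP*

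**What the plan says.** Section 4.3.4 (Clinical laboratory) opens with "Blood sampling and sample analysis is performed at the clinical centre". The list below that sentence includes 25(OH)D3 at baseline and every 6 months, and at the 3-monthly visits "25(OH)D3 serum levels, in case of drug interruption when serum 25(OH)D3 levels are > 80 ng/ml". Genotyping is handled differently: "SNP analysis will be performed by the laboratory of [name], VIB", with call-rate and duplicate checks. No common assay, calibration or central laboratory is stated for 25(OH)D3.

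The trial is multicentre. The synopsis names Leuven "and other European academic sites", and section 4.3.9 says that "a multiple center study is necessary, via participation of other academic centers". Enrolment is planned from fall 2012 to fall 2023.

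Section 7.2 plans three kinds of analysis that use the level:

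- Genotype: "The evolution in 25(OH)D3 levels in function of genetic variability in the Vitamin D pathway will be analysed by a linear mixed model". The next sentence reads: "Sensitivity analyses will include patient's compliance, seasonal effects and patient's baseline characteristics like age and gender".
- Melanoma site and subtype: analysis of variance of the level at diagnosis, in newly diagnosed patients only. No covariates are named.
- Relapse: a joint model of the level over time and relapse-free survival. No covariates are named.

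No centre or laboratory term appears in any of the three. Further detail is left to a later statistical analysis plan, which is not among the documents.

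**The concern.** Genotype, melanoma site, subtype and attained level are not randomised, so the trial's randomisation does not balance them across centres. Suppose one laboratory reads higher than another, or patients at one site truly have higher levels, and the centres also differ in allele frequency or tumour case mix. A pooled analysis without a centre term then assigns part of the centre difference to genotype or subtype. A patient random intercept does not prevent this, because genotype varies between patients and not within them. Season does not stand in for laboratory.

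25(OH)D3 is a listed secondary endpoint, and whether the rise in level depends on genetic variability is a stated aim of the project (section 1.1). A false signal would therefore bear on a question the trial sets out to answer. It would not bear on the primary treatment comparison.

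**Working it through.** The plan gives no figure to reproduce. The check has two parts: what the text commits to, and how large the effect could be under stated assumptions.

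**Text.** The covariates compliance, season, age and gender belong to the mixed model only, as sensitivity analyses. The analyses of variance and the joint model have none. Centre is not a randomisation stratum (section 4.2: time of diagnosis only).

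**Genotype against level, one value per patient.** Assumed, since the documents give no assay data: n = 500 (the planned size), two laboratories with shares 60/40 (w = 0.4), within-laboratory SD 10 ng/ml, constant offset b, allele frequencies f0 and f1, no true genotype effect. With c the centre indicator and g the allele count:

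- cov(c, g) = w(1−w)·2(f1−f0)
- var(g) = (1−w)·2f0(1−f0) + w·2f1(1−f1) + w(1−w)·4(f1−f0)²
- spurious slope = b·cov(c, g)/var(g)
- SE ≈ √[(SD² + w(1−w)b²)/(n·var(g))]
- z = slope/SE; rejection rate = P(Z > 1.96−z) + P(Z < −1.96−z)

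For b = 4 and frequencies 0.30 and 0.40: cov = 0.24 × 0.20 = 0.048; var(g) = 0.252 + 0.192 + 0.0096 = 0.4536; slope = 4 × 0.048/0.4536 = 0.423 ng/ml per allele; SE = √(103.84/226.8) = 0.677; z = 0.626; rejection rate 9.6%. For 0.30 and 0.50: cov = 0.096 and var(g) = 0.252 + 0.200 + 0.0384 = 0.4904. The simulated columns use 4,000 runs per case.

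| Offset (ng/ml) | Allele frequencies | Spurious slope | SE | Formula | Simulated, no centre term | Simulated, centre term |
|---|---|---|---|---|---|---|
| 4 | 0.30 / 0.40 | 0.423 | 0.677 | 9.6% | 9.6% | 5.2% |
| 6 | 0.30 / 0.40 | 0.635 | 0.692 | 15.1% | 15.8% | 5.3% |
| 4 | 0.30 / 0.50 | 0.783 | 0.651 | 22.5% | 21.0% | 4.7% |
| 6 | 0.30 / 0.50 | 1.175 | 0.666 | 42.3% | 41.9% | 4.6% |
| 4 | 0.30 / 0.30 | 0 | 0.703 | 5.0% | 5.2% | 4.9% |

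**Repeated measures, mean level.** With five visits and assumed between- and within-patient SDs of 8 and 6 ng/ml, the SD of a patient mean is √(64 + 36/5) = 8.44. The same formula gives 11.4%, 18.8%, 29.3% and 53.9% for the four unequal-frequency cases. Averaging visits therefore does not dilute the problem. Simulation gives 10 to 53% without a centre term and 4 to 6% with one.

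**Repeated measures, change.** A constant offset cancels from each patient's slope. In the same setting, testing genotype against slope without a centre term rejects 4.9 to 5.2% of the time. A proportional assay bias does not cancel fully: 15% bias gives about 6 to 10%.

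**Other centre structure, and subtype.** A separate simulation assumed three centres (60/20/20), mean 22 and SD 9 ng/ml, proportional assay bias of 10 to 30%, and 600 runs per case (Monte Carlo error about 1 to 2 points).

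- Genotype, n = 500: 5.8 to 16.7% for a 10-point frequency gap and 10.8 to 42.3% for a 20-point gap.
- Two-category subtype, n = 167 (one third of 500, assumed): 5.0 to 7.3% and 6.0 to 11.0%.
- With a centre term: 4.3 to 6.5% in all of these cases.

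**Level and relapse.** The only run had 60 repeats per case and is too noisy to quote. The effect in the joint model is argued by the same mechanism but has no number.

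**The case against.** Several objections have force.

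- *Local measurement is an inference.* The sentence in section 4.3.4 does not say that every centre uses its own assay. The table of contents lists a page of study core facilities that is not in the text reviewed and could name a common laboratory. Local analysis is the natural reading, but a reader who takes it as established goes further than the text.
- *The bias needs two conditions together.* Levels must differ by centre, and so must allele frequency or case mix. The documents show neither. Recording "country of birth of all four grandparents" (section 4.3.1) makes an ancestry adjustment possible; it does not show that ancestry differs by centre. A reader might infer that centre is a confounder in all three analyses. The documents support only that it can be.
- *The large figures concern mean level.* Section 7.2 speaks of evolution. If the genotype question is purely one of slope, a constant offset does no harm and a proportional bias does little. This stands. However, section 7.2 does not restrict the model to slopes, and a genotype main effect in it is a between-patient contrast.
- *The covariate list is open and a later plan will follow.* This is true, and a centre term can still be added there. But nothing commits to it, and no later plan can adjust for an assay change that was never recorded.
- *Full adjustment could be too heavy.* The number of centres is not given. A hazard ratio of 0.40 at 90% power (two-sided 5% assumed) needs only 4(1.960 + 1.282)²/(ln 0.40)² ≈ 50.1, so 51 events (Schoenfeld), or (1.4/0.6)²(1.960 + 1.282)² ≈ 57.2, so 58 (Freedman). One fixed effect per laboratory and assay period in the survival part could be sparse. Centre terms also absorb real differences in vitamin D status between sites. Both points shape the fix.

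A reader might also infer that the primary result is at risk. It is not: treatment is randomised, and relapse is not defined by the assay.

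**Conclusion.** The point holds in a conditional form. As written, section 7.2 offers no protection against centre or laboratory differences in any 25(OH)D3 analysis, and section 4.3.4 gives reason to expect that such differences are possible. How large the resulting bias would be in this trial cannot be known from the documents.

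For genotype against mean level, the false-positive rate is about 10 to 50% under the assumed 4 to 6 ng/ml offsets and 10- to 20-point frequency gaps, and close to 5% once centre is in the model. It is also close to 5% if allele frequencies are equal across centres. For within-patient change the effect is nil (constant offset) or small (proportional bias). For subtype it is about 5 to 11%, and at a 10-point gap hardly distinguishable from nominal. For the joint model it is unquantified. The matter is confined to secondary and mechanistic analyses, but the remedy is cheap enough to adopt before database lock.

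**What to change.** 1. Record the measuring laboratory and the assay with each 25(OH)D3 result, so that a change of method during the long enrolment period is visible.
2. In section 7.2, or in the statistical analysis plan before database lock, include centre or laboratory in the main mixed model. Add a centre-by-time term, or a sensitivity analysis with one, to cover proportional assay bias.
3. Include the same term in the site and subtype analyses of variance and in the longitudinal part of the joint model.
4. In the survival part of the joint model, handle centre by a random effect, by stratification or in a sensitivity analysis, because events may be few.
5. If one laboratory measures all samples, state this in section 4.3.4 and keep the centre term for differences between sites.

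The cost is one data field, a few sentences, and some degrees of freedom; how many depends on the number of centres, which is not given. Some genuine between-site variation in level will also be removed, which narrows the contrast available to the level-relapse analysis.
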